assess women's need for well-woman primary care, then refer and provide an appointment for care for women who desire one.

Specific Aims

Aim I. To determine if introducing a self-administered Reproductive Life Planning Tool (RLPT) with postpartum mothers during the 2-month WBV will increase the proportion of women receiving a well-woman primary care health visit by 6 months postpartum.

Aim Ia. To determine if introducing a self-administered Reproductive Life Planning Tool (RLPT) with postpartum mothers during the 2-month WBV will increase utilization rates of contraception by 6 months postpartum.

Aim II: To assess the extent of system adoption as well as patient-, provider-, and systems-level barriers and facilitators to integrating a self-administered Reproductive Life Planning Tool designed to facilitate referral of postpartum women for primary well-woman care within the context of a pediatric clinic.

Study Design and Intervention

This is a single-site system-level pilot study to measure the impact of a self-administered RLPT (attachment) during the 2-month WBV on PP women's subsequent receipt of primary health care and contraception, compared to usual care. To facilitate women's uptake of a referral for well-woman primary care, women will be offered the opportunity to schedule a visit for herself on the same day as her infant's next WBV or the first available visit if she needs more immediate care. This study will have two phases: **phase 1** is enrollment of a control or baseline group, followed by a washout period; **phase 2** is enrollment of the intervention group (intervention).

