Participant Eligibility: Postpartum women 15-49 years presenting with their infants to the CYC or PCAC for a 2-month WBV, and who also receive their own care at UIC (needed for chart abstraction purposes), are eligible to participate in the study. Women must be English and Spanish speakers.

Participant Exclusion: Women who are currently pregnant, less than 15 years or older than 49 years of age, or do not speak English or Spanish.

Participant Recruitment into the Research Study: The intervention is planned as a system-level intervention, thus, all women whose infants are scheduled for a 2-month WBV during the intervention period will have the opportunity to be exposed to the RLPT intervention. On study recruitment days (randomly selected half-days during phase 2), women whose infants are scheduled for a 2-month WBV will be approached by a

research assistant (RA) who will screen for eligibility. Recruitment into the study will occur before, during or after the WBV, baseline surveys will be completed during or after the WBV to avoid biasing women's responses on the RLPT, which is administered *prior* to the WBV. If a woman is eligible and interested in participating, she will be consented and asked if she has time to complete a baseline survey. The baseline survey will include the domains listed in Table 1. To the extent possible, the baseline survey will be self-administered using a tablet computer linked to the RedCap database. A study RA will be available to provide assistance or administer the survey if necessary. When possible, the surveys will be completed immediately after the WBV in a private room. We are sensitive to the fact that women may not have the time to stay after the WBV, in which case we will request permission to conduct the survey by phone at a convenient time. Our research team has extensive experience recruiting PP participants and we have found this to be an effective strategy. Because this is a system-level intervention, women who decline participation in the study will still receive the intervention but will not participate in any research data collection. For example, a woman who does not agree to participate in the study would still have been given the RLPT prior to the infant's visit and, if desired, she will receive a referral and appointment for care though she will not be included in the study.

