with pediatricians weekly during the first 4 weeks of the study, and monthly thereafter, to answer questions and encourage consistent provider use of the tool. We will schedule a ‘refresher’ training 3 months after the start of the study to reinforce appropriate use of the tool. During the training, physicians will be instructed on how to start a conversation with women, what to document on the tool, and how to initiate a referral if needed. Physicians are *not* expected to provide contraceptive counseling to mothers, only to engage women in a discussion about their health care needs. An information sheet about the study will be given to all pediatric providers who are trained.

Selection of control group: The control group will be enrolled during phase 1 (first 4 months) prior to the introduction of the intervention. Similar to the intervention group, women will be recruited by an RA before, during or after the health care visit and screened for eligibility. Informed consent will be obtained for a baseline survey using the same procedure as described for the intervention group (same gift card amounts). Because we are studying health behaviors, we cannot share the specific aims of the study with control group participants as this could bias behavior. The control group participants will be told that this is a study monitoring women’s general health care experiences at UIH. After enrollment of the control group, a 6-week washout period prior to phase 2 (intervention) will ensure women are not enrolled into both arms of the study.

Sample: This pilot study will enroll at least 50 women per group. This sample size will provide a stable estimate of the intervention’s effect on primary care receipt by 6 months postpartum for power calculations for a larger, subsequent study of intervention effectiveness. There are approximately 200 deliveries per month at UIH, with 57% (114) of these infants having a 2-month WBV at UIH. For the 4-month period of recruitment each for control and intervention groups, we can meet our target enrollment of 50 in each group by recruiting women during four of the ten half-day CYC clinics per week, assuming a conservative participation rate of 40%.

Table 1 Study Variable Table

Variable	Specific Aim	Level of Measurement	Time of Collection	Tool	Variable Type
Demographic Data	I	Women	Enrollment	Baseline survey	Covariate
Physician Characteristics Male/Female, Trainee/Faculty	II	Physicians	Enrollment	Medical record schedule	Covariate

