Clinical Operations Visit time and day of week	II	Health System	Enrollment	Medical record schedule	Covariate
Health and Family Planning					
Women’s general health status	I	Women	Enrollment	Baseline Survey	Covariate

Women's general health behaviors (smoking, alcohol, nutrition and exercise)	I	Women	Enrollment	Baseline Survey	Covariate
Plans for future pregnancy	I	Women	Enrollment	RLPT	Covariate
Current contraception type and use	I	Women	Enrollment	RLPT	Covariate
Pregnancy status	I	Women	6 months postpartum	Phone survey and Chart review	Dependent
Referral to primary care	I	Women	Enrollment	RLPT	Dependent
Receipt of primary care visit	I	Women	6 months postpartum	Phone survey and Chart review	Dependent
Use contraception, duration and method	I	Women	6 months postpartum	Phone survey and Chart review	Dependent
Feasibility, Acceptability, and Adoption of RLPT					
Ease of use, comfort and satisfaction with tool	II	Physician	Year 2	Focus groups	Acceptability
Ease of use, comfort and satisfaction with tool	II	Women	Enrollment	Baseline survey	Acceptability
Women's need and desire for referral	I and II	Women	Enrollment	RLPT	Acceptability
Women's barriers and facilitators	II	Women	6 months postpartum	Phone survey and Chart review	Feasibility
Physician barriers and facilitators	II	Physician	Completion of study	Focus groups	Feasibility
Completion rate for grey box on RLPT form	II	Health System	Enrollment	RLPT completion rate by women and physicians	Adoption

Data Sources and Collection

Surveys of Women: All participants will complete a baseline survey (English and Spanish) at the time of enrollment in the study (during or after the WBV) and will receive

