a phone call at 6 months PP for the follow-up survey (survey and interview questions domains listed in Table 1). During the baseline survey, in addition to demographic information, women will be asked about their general health status and health behaviors, and current contraception type and use. Those in intervention arm will be asked about their experience completing the RLPT during the WBV, referral to well-woman primary care (if applicable). For the follow-up survey we will try to reach each participant as close to 6 months as possible, but no later than 9 months PP. Structured phone interviews with women will include questions from the following domains: 1) use of health care services; 2) use and type(s) of contraception; and 3) known pregnancy status. The intervention group interviews will also include experience completing the RLPT during the WBV; and, the process of getting care (for those who chose to do so) (SA II). To verify RLPT exposure at the individual level, the RLPT tool will be linked to the mother using the patient sticker placed on the tool.

Medical Records: Medical records will be reviewed at baseline and at 6 months PP to determine receipt of health care services and contraception. We recognize that some women may receive additional health care outside the UIC system; for this group, we will not be able to confirm medical visits outside the UIC system.

Focus Groups with Providers: We will conduct two in-depth qualitative focus groups with physicians (residents and faculty) after the intervention is complete during study year 2. The focus group guide will include questions from the following domains: 1) Experience implementing the RLPT; and, 2) barriers and facilitators to implementation of RLPT (SA II). In addition, study investigators will keep a running log of barriers and facilitators experienced throughout the intervention implementation period.

Data Management

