All survey data will be directly entered into REDcap web-based data capture screens that will be programmed and tested prior to the study. Data will be imported to SAS for analysis. Variables (Table 1) will be merged across time point by study ID and cleaned and recoded. Focus groups will be recorded, transcribed, and uploaded to DeDoose qualitative analysis software. Completion of the Grey Box (physician section of the tool) will be a measure of provider “adoption” of the intervention; completion rates will be tracked by comparing completed forms with completed clinic visits for 2-month WBVs. Completed clinic visit data are available in our existing medical record scheduling system.

Analysis

Specific Aim I and Ia: Baseline characteristics will be assessed for equivalency across groups using chi-square tests for categorical and t-tests for continuous variables. Unbalanced characteristics will be adjusted for in further analyses. The primary outcome, receipt of primary care services for women by 6 months PP (SA I) will be ascertained both by self-report during the 6-month phone interview and by medical record review, in order to minimize missing data. Evidence of a visit from either source

will be counted as receipt. Utilization, type and duration of contraception (SA 1a) by 6 months PP will be assessed similarly. An intent-to-treat analysis will be performed for SA I and 1a. A crude relative risk (RR) and risk difference (RD) will be calculated with 95% confidence intervals to estimate the effect of the intervention on primary outcomes. If adjustment is needed for covariates, RRs and RDs will be estimated using the average marginal predictions from a fitted logistic regression model with the following form:⁴¹

$$\text{logit}(y) = \beta_0 + \beta_1x_1 + \beta_2x_2 + \dots + \beta_kx_k, \text{ where:}$$

y =	SA 1: Woman's primary care visit by 6 months (1 = Yes/0 = No)
	SA 1a: Use of contraception at 6 months (1 = Yes/0 = No)
x ₁ =	RLPT Intervention (1 = Intervention/0 = Control)
x ₂ – x _k =	Unbalanced covariates

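### The primary outcome has no start date, so visits made before the RLPT count as receipt; the bias depends on whether prior visits differ between the two phases

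*Combined protocol and SAP*

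**What the plan says.** - **Specific Aims, Aim I:** the RLPT is meant to "increase the proportion of women receiving a well-woman primary care health visit by 6 months postpartum". An end is given, but no start.
- **Table 1:** the row "Receipt of primary care visit" is collected at 6 months postpartum, again without a start. No row records a visit made before enrollment.
- **Analysis, Specific Aim I and Ia:** "The primary outcome, receipt of primary care services for women by 6 months PP (SA I) will be ascertained both by self-report" and by chart review. A visit found in either source is enough, and the model outcome carries the same 6-month limit. No condition is placed on the visit date. Covariates enter the model only if they are found unbalanced between groups.
- **Study Design and Intervention:** the stated purpose is the effect of an RLPT given at the 2-month WBV on "subsequent receipt of primary health care and contraception, compared to usual care".
- **Participant Exclusion:** "Women who are currently pregnant, less than 15 years or older than 49 years of age, or do not speak English or Spanish". Women who have already had their own visit are not excluded.
- **Selection of control group:** "The control group will be enrolled during phase 1 (first 4 months) prior to the introduction of the intervention". A 6-week washout and then the intervention phase follow.
- **Medical Records:** "Medical records will be reviewed at baseline and at 6 months PP to determine receipt of health care services and contraception". The same paragraph concedes that visits outside the UIC system cannot be confirmed.
- **Sample:** the pilot is to estimate the intervention's "effect on primary care receipt by 6 months postpartum for power calculations for a larger, subsequent study of intervention effectiveness".

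**The concern.** The tool is handed over at about 2 months and the outcome closes at 6 months, so roughly a third of the outcome window lies before exposure. Visits in that part are scored as receipt in both arms. The design statement concerns care that follows the tool, but the aim, the variable table, the scoring rule and the model do not carry that restriction.

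Two things are at stake. First, the rates and the relative risk handed to the planners of the larger study would mix care the tool could influence with care it could not. Second, the arms are enrolled one after the other and are not randomised. A systematic difference between phases in the share already seen would appear in the risk difference as if it were an effect. The plan does not say that this share will be reported, so a reader could not tell.

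A lesser point concerns the other end of the window. Follow-up calls may run to 9 months postpartum, and no described step applies the 6-month limit to self-reported visits. The survey form is not in the text and may already do so.

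**Working it through.** **Inputs from the documents.** There are at least 50 women per group (Sample). The plan's recruitment figure reproduces: 200 × 0.57 = 114 two-month WBVs a month, and 114 × 4 months × 0.4 of clinics × 0.4 participation = 73, above 50. No expected receipt rate or effect size is given, so there is no planned effect to reproduce.

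**Not in the documents.** The share with a visit before the index WBV, q, is not given. It may be small if only well-woman or internal-medicine visits count (referrals go to internal medicine). It may be large if the obstetric postpartum visit counts. For that visit the Background gives attendance below 53.7% in Illinois Medicaid, and elsewhere non-attendance of 11% to 40%, which is attendance of 60% to 89%.

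**Assumed for illustration.** Post-index receipt is 20% without the tool and 45% with it; n = 50 per arm.

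**1. Equal q.** The plan's outcome has P = q + (1 − q)p, so RD = (1 − q)(p1 − p0).

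| q | Control | Intervention | RD (points) | RR |
|---|---|---|---|---|
| 0.10 | 28.0% | 50.5% | 22.5 | 1.80 |
| 0.30 | 44.0% | 61.5% | 17.5 | 1.40 |
| 0.537 | 63.0% | 74.5% | 11.6 (unrounded rates) | 1.18 |

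If already-seen women respond as others do, the post-index outcome gives RD 25.0 and RR 2.25. If they do not respond at all, then at q = 0.30 the RD is 0.70 × 25 = 17.5 under both definitions and only the RR differs. It is 1.40 under the plan, against 31.5/14.0 = 2.25 (none of them returns) or 37.5/20.0 = 1.88 (20% return in both arms).

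**2. Unequal q, no effect.** False RD = (q1 − q0)(1 − 0.20).
- 5-point gap: 4.0 points.
- 10-point gap: 8.0 points, for example 24% vs 32% at q 0.05/0.15, or 44% vs 52% at q 0.30/0.40. The sign reverses if the gap does.
- 95% half-width: 1.96 × √[(0.44 × 0.56 + 0.52 × 0.48)/50] = 19.5 points, or 17.5 for 24% vs 32%. The shift would not stand out.
- Chance differences in q are already covered by that interval (one SD at q = 0.30 is √(2 × 0.21/50) = 9.2 points). Only a systematic phase difference is bias beyond it.

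**3. Post-index outcome without adjustment.** P = q·s + (1 − q) × 0.20, where s is the return rate of already-seen women. At q 0.30 vs 0.40:
- s = 0: 14.0% vs 12.0%, RD −2.0 points.
- s = 0.2: 20.0% vs 20.0%, RD 0.
- s = 0.4: 26.0% vs 28.0%, RD +2.0 points.

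Re-dating alone reduces the error in this example but does not remove it.

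**4. Adjusting only when a balance test fires.** The plan gives no threshold; 0.05 is assumed. Uncorrected chi-square gives p = 0.29 for 15/50 vs 20/50 and p = 0.041 for 15/50 vs 25/50. At true q 0.30 vs 0.40 the test fires in 18% of pilots (exact binomial enumeration). With the plan's outcome, the mean false RD left is 4.6 of the 8.0 points. At a threshold of 0.10 it fires in 29% and leaves 3.2 points.

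Always adjusting leaves 0 here, but only because the post-index rate was set equal in both phases.

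**The case against.** The strongest reply is that an outcome counted from delivery to 6 months is legitimate and is what Aim I names. Pre-index visits count in both arms, and only a phase difference in q biases the comparison. That stands. A reader might infer that the missing start date by itself makes the primary comparison invalid; the documents do not support that.

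Nor do they show that the phases differ. Both groups come from the same clinics under the same eligibility rule, in 4-month periods 6 weeks apart. The 5- and 10-point gaps above are assumed.

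A reader might also take 53.7% as a documented ceiling for q. It is not: it describes postpartum visits in a statewide Medicaid population, the Background also cites higher attendance, and the protocol elsewhere treats postpartum care as distinct from well-woman care. If only the latter counts, q may be small.

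It can also be said that the baseline chart review might supply a prior-visit characteristic to the balance check. The text does not rule this out. But Table 1 does not list it, no analysis names it, charts miss outside care, and a test-triggered rule would often leave it out.

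Finally, this is a feasibility pilot, and 4 to 8 points lie inside its own uncertainty. That limits the urgency. But the estimate's stated use is planning the larger study, so the outcome it measures should be settled.

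**Conclusion.** The gap in the definition is certain from the text: no start date, no exclusion, no prior-visit covariate and no stated analysis of earlier visits, against a design statement about subsequent care. Its size is unknown.

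- **Equal q:** no bias for the cumulative outcome. The RR is pulled toward 1, and the RD shrinks only to the extent that already-seen women would have responded to the tool.
- **Unequal q:** the gap passes into the RD, at 0.8 points per point of gap under the assumed 20% post-index rate.

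A reader might infer that re-dating the outcome and adjusting for prior visits would cure the historical-control design. It would not: a phase difference in care after the index visit would remain. The point is worth correcting because the change is cheap and the baseline charts are already to be reviewed. The evidence does not show that the pilot's result would be wrong.

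**What to change.** 1. In both arms, define the primary outcome as a primary care visit dated after the index 2-month WBV and by 6 months postpartum. State whether an obstetric postpartum visit counts.
2. Report any visit by 6 months postpartum alongside it, to match Aim I.
3. Record the woman's own visit between delivery and the index WBV from the planned baseline chart review, supplemented by a self-reported date because charts miss care outside UIC. Add it to Table 1 and adjust for it whatever the balance test shows. Where all or none of the already-seen women score 1 (always so for the outcome in item 2), the logistic term cannot be estimated; obtain the RR and RD by standardising over the two prior-visit strata.
4. Ask the date or month of each self-reported visit, so that the 6-month limit can be applied to late calls.

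**Cost:** outcome wording, one Table 1 row and the visit-date questions.

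**Downsides:**
- A lower event rate: with q = 0.30, control 14% to 26% (s from 0 to 0.4) instead of 44%.
- One more model term with about 50 women per arm.
- Recall error in dates.
- A score of 0 for a woman seen just before the WBV who needs no further visit.
- A small risk that a new baseline question prompts controls to seek care. Asking it at the follow-up call avoids this.

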During the WBV, physicians will review the information provided by the woman on the RLPT about general health, reproductive plans, and use of contraception. The pediatrician will use the RLPT to initiate a brief conversation with mothers about the need for a referral for well-woman primary care. We expect this conversation to take less than 3 minutes based on previous studies.²² We will create a referral process to the UIH Primary Care Plus clinic (internal medicine) through our electronic medical record. At the close of the WBV, if the mother desires a referral the pediatrician can request the referral during the infant's check-out process. Research staff will routinely review all referral needs and initiate scheduling based on the mother's preference. Women will be asked if they prefer the **next available** appointment or an appointment on the **same day as their infant's next WBV**. For women who desire their health care visit on the same day as their infant's next WBV (the 4-month visit), we will schedule both visits on the same day. To the extent possible, the mother's appointment will be earlier the same day (ideally 2 hours before) of the infant's scheduled visit, to promote attendance. We expect that by offering women the opportunity for a primary care visit on the same day as their infants' next WBV, the likelihood of adherence will be much greater than just offering a referral. Among women scheduled for care, if by the date of their infant's next WBV the woman has not attended her visit (she cancels or does not show), the research staff will contact her to reschedule, offering either the first available appointment or co-scheduling with the infant's next WBV.

Reproductive Life Planning Tool: We have created a RLPT (in English and Spanish) based on detailed feedback from physicians and women regarding how best to operationalize a RLPT in the pediatric setting (previous research studies).

Study site: The CYC and PCAC are comprehensive pediatric clinics; patients can be seen by a pediatric faculty member (faculty practice) or by a pediatric resident physician with direct supervision by a faculty member. The clinics serves a predominantly low-income Medicaid-insured population.

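### The either-source rule counts a self-reported UIC/UIH visit as receipt even when the reviewed UIC chart shows none

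*Combined protocol and SAP*

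**What the plan says.** Analysis, Specific Aim I and Ia, takes receipt of primary care by 6 months postpartum from both the phone interview and the record review, "in order to minimize missing data". The scoring rule is that "Evidence of a visit from either source" "will be counted as receipt". It sets no condition on where the visit took place, says nothing about a report that disagrees with the chart, and plans no chart-confirmed analysis.

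Other sections bear on this:

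- Participant Eligibility limits enrolment to women "who also receive their own care at UIC (needed for chart abstraction purposes".
- Data Sources and Collection, Medical Records, accepts that some women also have care elsewhere and that "we will not be able to confirm medical visits outside the UIC system". No other class of visit is named as unconfirmable.
- Study Design and Intervention sends referrals in-house: "We will create a referral process to the UIH Primary Care Plus clinic (internal medicine) through our electronic medical record". It adds that "Research staff will routinely review all referral needs and initiate scheduling", and that scheduled women who have not attended by the infant's next visit are contacted again.
- Data Sources and Collection, Surveys of Women, lets the follow-up call run as late as 9 months postpartum. It also makes the content group-specific: "The intervention group interviews will also include experience completing the RLPT during the WBV".
- Selection of control group enrols controls in an earlier phase and withholds the specific aims from them.

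**The concern.** The reason given for using two sources is missing data. That reason covers visits outside UIC. It does not cover a reported UIC/UIH visit when the chart for that system has been reviewed and shows nothing. There the outcome is observed and the two sources conflict, and the rule settles every such conflict in favour of the report. (The protocol uses UIC and UIH interchangeably; I take the UIC record to cover the UIH clinics.)

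False positives that are equally common in both groups pull the RR and RD toward no effect. If they are more common in one group, they create or hide a difference. Inflation is plausible for three reasons. The interview content reveals the group and no masking of interviewers is described. Research staff schedule and re-contact referred intervention women. Co-scheduling can bring a mother to UIH on the day of her own appointment, so a missed visit may be misremembered as attended.

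Timing adds to this. A call at up to 9 months can pick up a visit made after 6 months unless the visit is dated.

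The Sample section says that the pilot's estimate will feed the power calculation of a larger study. The confidence interval reflects random error but not this bias, so the bias would carry forward unseen.

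**Working it through.** The plan states no over-report rate, no expected receipt and no follow-up contact rate, so it has no figure of its own to reproduce on this point. The only input from the documents is n = 50 per group (Sample, a minimum). The rest is assumed.

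**Assumed inputs.** True receipt p = 40%; share reached by phone r = 80%; over-report f among reached women with no visit of 5% in controls and 10% to 20% in the intervention group; every false report names a UIC/UIH visit.

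**1. Apparent rate** = p + (1 − p) × r × f

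- f = 5%: 0.40 + 0.60 × 0.80 × 0.05 = 0.424
- f = 10%: 0.40 + 0.60 × 0.80 × 0.10 = 0.448
- f = 20%: 0.40 + 0.60 × 0.80 × 0.20 = 0.496

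**2. No true effect, more over-report in the intervention group**

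- RD: 0.448 − 0.424 = +2.4 points, up to 0.496 − 0.424 = +7.2 points
- RR: 0.448 / 0.424 = 1.06, up to 0.496 / 0.424 = 1.17
- Extra apparent successes: 50 × 0.024 = 1.2 women, up to 50 × 0.072 = 3.6 women

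**3. No true effect, more over-report in controls.** With 10% in controls and 5% in the intervention group, RD = 0.424 − 0.448 = −2.4 points.

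**4. True effect, equal over-report.** Take true rates of 40% and 55% and f = 10% in both groups.

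- Controls: 0.448. Intervention: 0.55 + 0.45 × 0.80 × 0.10 = 0.586
- RD falls from 15.0 to 13.8 points; RR falls from 0.55 / 0.40 = 1.38 to 0.586 / 0.448 = 1.31

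**5. Range over the true rate.** Set r = 1 and f = 5% against 15%, so that RD = (1 − p) × 0.10. The last column is the chance that a two-sided 5% comparison of 50 with 50 falsely favours the intervention; the nominal value is 2.5%.

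| p | Spurious RD | False benefit |
|---|---|---|
| 30% | 7 points | 10.8% |
| 40% | 6 points | 8.7% |
| 50% | 5 points | 7.2% |

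**6. Random error for scale.** The half-width of the 95% CI for the RD at p = 40% is 1.96 × √(2 × 0.40 × 0.60 / 50) = 0.192, about 19 points.

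**7. Why step 2 is an upper illustration for its rates.** With no true effect, RD = (1 − p) × r × (f_int − f_ctl). This applies the raised rate to every reached intervention woman without a visit. Scheduling is only for mothers who want a referral, and re-contact only for those scheduled. If only a fraction of the women carry the raised rate and the rest report as controls do, the RD shrinks in proportion. The part that a chart check can remove also shrinks with the share of false reports that name UIC/UIH.

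**8. What a place-specific rule could lose.** Assume outside-only visits in 15% of controls and 5% of the intervention group, 80% reached, and 20% of those visits misnamed as UIH.

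- Controls lose 0.15 × 0.80 × 0.20 = 2.4 points
- Intervention loses 0.05 × 0.80 × 0.20 = 0.8 points
- The RD moves by 2.4 − 0.8 = +1.6 points in favour of the intervention

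**The case against.** The rule is prespecified and has a stated reason. Accepting either source trades specificity for sensitivity, which is defensible in a feasibility pilot whose sampling error far exceeds the bias illustrated. This stands as a limit on importance. It does not explain why a conflict over a UIC/UIH visit should always go to the report.

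A reader might infer that the rule favours the intervention. The documents do not support that. They give no over-report rate in either group, and some features point the other way: a woman called to reschedule has been reminded that she missed the visit, and controls are told that the study monitors general care experiences at UIH, which might itself prompt reports of UIH visits.

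A reader might also infer that the chart is a definitive record, or that the plan throws it away. Neither holds. Nothing says that charts or their abstraction are complete, and care at UIC need not be exclusive. Chart-documented visits do count, and discordance could be tabulated from the two sources if the place of a reported visit is known.

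Two further points stand. The interview is described only by domain, so place and month may already be asked. And a place-specific rule has its own possible bias (step 8), which is why both results need to be shown.

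**Conclusion.** The point holds as a gap in the outcome definition: a reported UIC/UIH visit overrides a reviewed chart that shows none, and the missing-data reason does not reach that case. Using self-report for visits outside UIC is sound.

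The size and sign of any bias cannot be found from the documents. The spurious +2.4 to +7.2 points rests wholly on the assumed rates in the working, and is an upper illustration for those rates. The same formula gives a negative RD if controls over-report more, and dilution if over-report is equal. Next to a half-width of about 19 points the effect is modest, so this is an inexpensive improvement and not a defect that undermines the pilot.

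**What to change.** - Make sure the follow-up interview records the place and month of each reported visit.
- In Analysis, Specific Aim I and Ia, count a reported UIC/UIH visit only if the chart confirms it by 6 months postpartum. A visit found in the chart in that window counts as now.
- Accept self-report alone for visits outside UIC by 6 months postpartum.
- Prespecify the either-source result as a sensitivity analysis beside the primary result, and report the number of unconfirmed UIC/UIH reports by group.

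The cost is a short change to the analysis text and at most two interview items; no extra participants or data sources are needed. Place and month should be settled before follow-up calls begin, because they are hard to recover afterwards.

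The downside is that a true outside visit misnamed as UIH, or a visit missed in abstraction, would be lost, possibly unequally by group. The side-by-side results would show how much this matters. False reports of outside visits would remain under either rule.
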